## VIVAER: CORRELATION OF SYMPTOMS & FINDINGS

Nasal obstruction that is not responding to appropriate medical therapy may be an indication for surgery. Recently, the minimally invasive VivAer procedure may also be an option.

In a multi-center, prospective study, 89% of patients who underwent the VivAer procedure reported improved sleep quality, and 94% of patients reported improved ability to breathe through their nose during exercise or exertion. Furthermore, there was a 97% overall response rate with a 67% reduction in Nasal Obstruction Symptom Evaluation (NOSE). No serious adverse events were reported with the use of VivAer. While impressive, these positive outcomes were measured using patient symptom scores.

In patients with nasal obstruction, we propose to assess the objective improvement in nasal airflow secondary to the VivAer procedure. In an open-label, prospective single center study, patient questionnaires and objective measurements prior to and after the VivAer procedure will be conducted.

### **BACKGROUND AND SIGNIFICANCE**

The VivAer intranasal remodeling treatment is a minimally invasive procedure, which uses a stylus to deliver controlled and targeted low energy radiofrequency heating to the nasal sidewall to gently reshape the tissues. Unlike most established treatments, it is an outpatient intervention administered under local anesthesia. The investigators of this study are each fellowship trained in rhinology and skull base surgery and not only understand which patients would benefit most from this treatment, but also be able to deliver the treatment safely.

### **Specific Aims:**

- Eligible patients will show significant clinical improvement on the following patient questionnaires and on objective measurements.

## VIVAER: CORRELATION OF SYMPTOMS & FINDINGS

### **Specific Aim 2:**

- Improvement in Nasal Obstructive Symptom Evaluation (NOSE) score

### **Specific Aim 3:**

- Improvement in SinoNasal Outcome Test (SNOT)-22 score

## **RESEARCH DESIGN AND METHODS**

### **Study Design:**

This is a prospective, non-randomized trial to assess objective improvement in nasal patency after undergoing treatment of the nasal valve with VivAer. Up to twenty-six subjects will be enrolled in this trial. Patients presenting with nasal obstruction and no notable septal deviation will be instructed to complete four weeks of intranasal steroid sprays. After patients complete the intranasal steroid spray, they will return to the clinic to assess nasal patency. If nasal obstruction symptoms persist, their eligibility for the VivAer procedure is assessed. The inclusion and exclusion criteria outlined below will be reviewed. If the patient is eligible and interested in receiving the VivAer procedure, they will be consented and receive a date to undergo the procedure. At the procedure date, they will perform baseline peak nasal inspiratory flow (PNIF) measurements and complete baseline Sino-Nasal Outcome Test (SNOT-22) scores and Nasal Obstructive Symptom Evaluation (NOSE) scores. After the procedure, subjects will be off steroid sprays for 2 weeks and will only use nasal saline irrigations during the procedure-recovery period. Subjects will return to clinic for evaluation at 4 weeks, 12 weeks and 24 weeks post procedure and during each of these visits will complete interval PNIF measurements, SNOT-22 scores, and NOSE scores.

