## VIVAER: CORRELATION OF SYMPTOMS & FINDINGS

### **Eligibility:**

#### **Inclusion Criteria:**

1. Adults 18 years and older seeking treatment for nasal obstruction and willing to undergo an office-based procedure.
2. Nasal obstruction, defined as  $\geq 60$  by the NOSE scale.
3. The nasal valve is the primary or significant contributor to the subject's nasal obstruction as determined by the investigator, based on clinical presentation, physical examination, or nasal endoscopy.
4. Subjects has symptomatic improvement with use of external or internal nasal dilators, Q-Tip or curette test (manual intranasal lateralization), or the Cottle Maneuver (manual lateral retraction of the cheek).
5. Subject experienced minimal symptomatic improvement after the four-week fluticasone steroid nasal spray regimen.

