### Study Calendar

	Consent	Procedure	Four Week Follow-up (One Month; +/- one week)	Twelve Week Follow-up (Three Months; +/- 2 weeks)	Twenty-four Week Follow-up (Six Months; +/- 2 weeks )
Exam	X		X	X	X
Determine Eligibility	X				
Procedure		X			
PNIF Measurements	X		X	X	X
SNOT-22 Questionnaire	X		X	X	X
NOSE Questionnaire	X		X	X	X
Adverse Event Monitoring		X	X	X	X

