## VIVAER: CORRELATION OF SYMPTOMS & FINDINGS

(Fig. 2). No incisions are made. Tissue temperature feedback is constantly provided by the stylus before, during and after treatment to allow the generator to modulate power for maintaining treatment temperature at 60°C, and procedure safety.

Each treatment cycle consists of an 18-second treatment pulse and 12-second cooling time while applying continuous upward pressure with the stylus in an outward direction perpendicular to the upper lateral cartilage at each position. A standardized approach is used based on animal and human pilot studies where temperature and duration parameters were determined for optimal safety and efficacy

Efficacy endpoint will be determined at 26 weeks using the NOSE and SNOT survey scores. Scores are assessed at baseline, 4, 12, and 26 weeks post procedure and the responder rate, defined as a  $\geq 15$ -point decrease, was determined. In two studies, the minimally clinically important difference (MCID) in the NOSE score was calculated as approximately 4 to 6.3 points, so a  $\geq 15$ -point was selected as the minimal clinically relevant change.

Additionally, peak nasal inspiratory flow (PNIF) meters will be used at baseline, 4, 12, and 26 weeks.

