### **Statistical Analysis:**

Patient characteristics, objective measurements and patient questionnaires will be summarized using descriptive statistics such as mean with standard deviation and mean or frequency with percentage. Comparisons of outcomes measured between baseline and postop will be assessed using the paired t-test or McNemar's test. A total of 26 patients is required to achieve 80% power for a paired t-test with a significance level of  $\alpha=0.05$  and a moderate effect size of  $d=0.50$ . All statistical analysis will be performed using SAS 9.4 (SAS Institute, Cary, NC) with two-sided tests and  $p<0.05$  considered statistically significant.

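### The Study Design text and the Study Calendar put baseline at different visits, and the Calendar's choice would probably let regression to the mean count as NOSE improvement

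*Combined protocol and SAP*

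**What the plan says.** The Study Design section separates two days. Eligibility is reviewed at a clinic visit after the four-week steroid spray course, and then "If the patient is eligible and interested in receiving the VivAer procedure, they will be consented and receive a date to undergo the procedure". Baseline belongs to the second day: "At the procedure date, they will perform baseline peak nasal inspiratory flow (PNIF) measurements and complete baseline Sino-Nasal Outcome Test (SNOT-22) scores", together with NOSE. No interval between the two days is given.

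The Study Calendar disagrees. Its PNIF and SNOT-22 rows and its "NOSE Questionnaire" row are marked under Consent, blank under Procedure, and marked again at the three follow-up visits. The row "Determine Eligibility" is marked under Consent only. Inclusion criterion 2 reads "Nasal obstruction, defined as" a NOSE score of 60 or more.

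The analysis text does not settle the matter. Statistical Analysis says "Comparisons of outcomes measured between baseline and postop will be assessed using the paired t-test" or McNemar's test and names neither visit. The efficacy paragraph in Description of Procedure defines response as a fall of at least 15 points and also refers to baseline without naming a visit.

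There is a smaller mismatch at the other end. The efficacy paragraph says "Efficacy endpoint will be determined at 26 weeks using the NOSE and SNOT survey scores", whereas Study Design says "Subjects will return to clinic for evaluation at 4 weeks, 12 weeks and 24 weeks post procedure" and the Calendar also gives 24 weeks.

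**The concern.** Every paired comparison and the responder rate start from baseline. Staff who follow the Calendar would collect a different baseline from staff who follow the text, and both kinds could end up in one 26-patient dataset. This applies to PNIF, SNOT-22 and NOSE alike and needs no assumption.

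The second problem is specific to NOSE. A group selected because a noisy score reached 60 contains some patients whose score was high by chance on that day. Their next score tends to be lower without any treatment effect. If the qualifying score is also the baseline, that fall enters the change score. The study is open-label and uncontrolled, so nothing in the design separates the fall from benefit. SNOT-22 and PNIF are not used for selection and are affected only as far as their same-visit errors correlate with the NOSE error.

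**Working it through.** **1. The passages side by side**

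| Source | Visit for pre-treatment PNIF, SNOT-22, NOSE |
|---|---|
| Study Design | Procedure date, after a separate consent visit |
| Study Calendar | Consent (same column as the eligibility row); Procedure blank |
| Description of Procedure, efficacy paragraph | Baseline, visit not named |
| Statistical Analysis | Baseline, visit not named |

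The Calendar's columns appear intact: the procedure itself is marked only under Procedure, and adverse event monitoring starts there. A table broken in extraction is therefore an unlikely explanation.

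**2. Inputs for the size of the bias**

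From the protocol: entry threshold NOSE 60, n = 26, two-sided 0.05, paired t-test, 15-point responder threshold. The protocol has no figure for the bias itself to reproduce.

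Assumed, because the documents do not give them: NOSE SD 20 among candidates, candidate mean 50 to 70, reliability (rho) 0.7 to 0.9, and independent errors between visits. Central values are mean 60 and rho 0.8. Inclusion criterion 5 (minimal improvement on the spray) is not modelled.

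**3. Expected spurious fall with no treatment effect**

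Fall = (1 − rho) × SD × φ(z) / (1 − Φ(z)), with z = (60 − mean) / SD.

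Central case: z = 0, φ/(1 − Φ) = 0.3989/0.5 = 0.798, so the fall is 0.2 × 20 × 0.798 = 3.19 points.

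| Candidate mean | rho 0.7 | rho 0.8 | rho 0.9 |
|---|---|---|---|
| 50 | 6.85 | 4.56 | 2.28 |
| 60 | 4.79 | 3.19 | 1.60 |
| 70 | 3.05 | 2.04 | 1.02 |

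With a separate baseline and independent errors the expected fall is about 0.

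**4. Simulation with no treatment effect** (3,000,000 candidates per scenario, scores limited to 0–100, selected at 60 or above, trials of 26)

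| | Qualifying score as baseline | Separate baseline |
|---|---|---|
| False-positive rate, range | 9% to 65% | 5% |
| False-positive rate, central | 26% | 5% |
| 15-point responders, range | 5% to 28% | 4% to 16% |
| 15-point responders, central | 16% | 11% |

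**5. Simulation with a true effect, central values** (qualifying score / separate baseline)

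| True fall | Power | Responders |
|---|---|---|
| 5 points | 91% / 49% | 28% / 21% |
| 10 points | 100% / 97% | 43% / 34% |
| 20 points | 100% / 100% | 74% / 65% |
| 40 points | 100% / 100% | 99% / 97.5% |

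The last row corresponds to the 67% NOSE reduction cited in the protocol's opening section: 0.67 × 60 = 40.2 points for a patient entering at 60.

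**6. SNOT-22 and PNIF, central values.** If their same-visit error correlates 0, 0.3 or 0.5 with the NOSE error, the spurious change is 0, 0.05 or 0.08 SD and the false-positive rate is 5%, 6% or 9%.

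**7. The 24/26-week label.** The Calendar window is 24 ± 2 weeks, that is 22 to 26, so week 26 falls inside it. The label needs reconciling, but no visit is lost.

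**The case against.** The strongest reply is that the bias depends on two conditions that the documents do not establish: that staff follow the Calendar, and that the qualifying NOSE is then used as baseline. Study Design is the only place that ties the word baseline to a visit, and it names the procedure date. It also reviews eligibility before consent, so a qualifying NOSE could already exist, with the Calendar's consent-visit NOSE collected after it. This stands as a limit on certainty, and it is why the conclusion says probably. It does not remove the problem, because no separate qualifying score is scheduled and the Calendar puts the eligibility decision and the only pre-treatment NOSE in the same column.

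The size is also open to challenge. The central fall of 3.2 points is below the 4 to 6.3 points that the protocol cites as the minimal important difference, and at the effect it cites from earlier work the conclusion is the same under either baseline. That is correct: the bias matters if the true effect is small.

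The figures also move with the assumptions. On a 5-point score grid the central false-positive rate is 22% and responders are 21% versus 16%. Reading criterion 5 as an improvement of at most 10 points raises the rate to about 50% on the ungridded scale. The direction is firm; the percentages are illustrations.

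Finally, a procedure-day score could differ from the consent-visit score for other reasons, since neither the interval nor spray use during it is specified. That is a reason to record the dates. It does not favour the qualifying score as baseline.

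**Conclusion.** The concern holds. The contradiction over when PNIF, SNOT-22 and NOSE are first measured is plain in the text, affects every outcome, and is not resolved by the analysis section.

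The NOSE bias is conditional on the Calendar being followed with the qualifying score as baseline. Its direction is then certain, and its size depends on inputs that the documents do not give. Under the stated assumptions it is a few points on the mean and a false-positive rate well above 5%. It would matter for a true effect of about 5 points and would not change the test result at about 40 points. The direct bias is confined to NOSE.

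This should be fixed before enrolment proceeds under two readings. The 24/26-week difference is a minor label correction.

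**What to change.** Correct the Study Calendar to match Study Design by marking PNIF, SNOT-22 and NOSE in the Procedure column, to be completed before the procedure starts. In the efficacy paragraph and in Statistical Analysis, state that:

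- these measurements are the baseline for all change scores and for responder status;
- the qualifying NOSE is used for eligibility only;
- an eligible patient whose baseline NOSE is below 60 stays in the analysis, since dropping such patients would bring the selection back.

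Record the date of the qualifying score so that the interval to baseline can be reported. Use one final time point throughout, for example by tying the efficacy endpoint to the scheduled 24-week (± 2) visit.

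The cost is wording plus one measurement set on a day the patient already attends. Observed NOSE improvement may be about 3 points smaller, and about 20% of baselines would fall below 60 (both at the central values).

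The fix is not complete if the two visits are close together and their errors are correlated. With an assumed error correlation of 0.5, a spurious fall of 1.6 points and a 10% false-positive rate remain at the central values.

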## VIVAER: CORRELATION OF SYMPTOMS & FINDINGS

### **Eligibility:**

#### **Inclusion Criteria:**

1. Adults 18 years and older seeking treatment for nasal obstruction and willing to undergo an office-based procedure.
2. Nasal obstruction, defined as  $\geq 60$  by the NOSE scale.
3. The nasal valve is the primary or significant contributor to the subject's nasal obstruction as determined by the investigator, based on clinical presentation, physical examination, or nasal endoscopy.
4. Subjects has symptomatic improvement with use of external or internal nasal dilators, Q-Tip or curette test (manual intranasal lateralization), or the Cottle Maneuver (manual lateral retraction of the cheek).
5. Subject experienced minimal symptomatic improvement after the four-week fluticasone steroid nasal spray regimen.

#### **Exclusion Criteria:**

1. Prior surgery to the nasal valve, rhinoplasty, septoplasty, inferior turbinate reduction or other surgical nasal procedures within the past 12 months.
2. Severe and/or chronic sinusitis, recurrent sinusitis, or allergies leading to nasal obstruction and currently requiring *oral* corticosteroid therapy.
  - a. Treated allergic rhinitis is not an exclusion criteria and eligible patients will be permitted to continue use of oral and/or topical medications throughout the trial.
3. Severe case of any of the following; septal deviation, turbinate hypertrophy, polyps, or ptotic nasal tip believed to be the primary contributor to the subject's nasal obstruction symptoms and warranting surgical intervention.

## VIVAER: CORRELATION OF SYMPTOMS & FINDINGS

4. Known or suspected allergies or contraindications to the anesthetic agents and/or antibiotic medications to be used during the study procedure session.
5. Known or suspected pregnancy, or lactation.
6. Other medical conditions that the investigator believed would predispose subject to poor wound healing or increased surgical risk.

### Study Calendar

	Consent	Procedure	Four Week Follow-up (One Month; +/- one week)	Twelve Week Follow-up (Three Months; +/- 2 weeks)	Twenty-four Week Follow-up (Six Months; +/- 2 weeks )
Exam	X		X	X	X
Determine Eligibility	X				
Procedure		X			
PNIF Measurements	X		X	X	X
SNOT-22 Questionnaire	X		X	X	X
NOSE Questionnaire	X		X	X	X
Adverse Event Monitoring		X	X	X	X

### Description of Procedure

The region of the upper lateral cartilage is anesthetized intranasally using either topical lidocaine 4% or tetracaine 4%. Lidocaine 1% with epinephrine is subsequently injected to achieve complete local anesthesia.

Bilateral radiofrequency treatment is applied in a single visit using Aerin Medical's VivAer Stylus with a Model ORA-50S generator (Fig. 1) at a setting of 60°C and 4 watts. The stylus is placed intranasally onto the mucosa overlying the lower edge of the upper lateral cartilage and three non-overlapping loci along the nasal valve angle are treated on each side

## VIVAER: CORRELATION OF SYMPTOMS & FINDINGS

(Fig. 2). No incisions are made. Tissue temperature feedback is constantly provided by the stylus before, during and after treatment to allow the generator to modulate power for maintaining treatment temperature at 60°C, and procedure safety.

Each treatment cycle consists of an 18-second treatment pulse and 12-second cooling time while applying continuous upward pressure with the stylus in an outward direction perpendicular to the upper lateral cartilage at each position. A standardized approach is used based on animal and human pilot studies where temperature and duration parameters were determined for optimal safety and efficacy

Efficacy endpoint will be determined at 26 weeks using the NOSE and SNOT survey scores. Scores are assessed at baseline, 4, 12, and 26 weeks post procedure and the responder rate, defined as a  $\geq 15$ -point decrease, was determined. In two studies, the minimally clinically important difference (MCID) in the NOSE score was calculated as approximately 4 to 6.3 points, so a  $\geq 15$ -point was selected as the minimal clinically relevant change.

Additionally, peak nasal inspiratory flow (PNIF) meters will be used at baseline, 4, 12, and 26 weeks.

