## **EXPECTED BENEFITS**

It is anticipated that this procedure will improve nasal breathing. VivAer is minimally invasive. The objective data received from this study will help clinicians provide better guidance to patients interested in receiving this treatment.

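### The stated purpose is objective nasal airflow, but the only efficacy endpoint is self-reported NOSE and SNOT; PNIF is tested yet has no endpoint role

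*Combined protocol and SAP*

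**What the plan says.** **Purpose.** The introduction reports earlier VivAer results and remarks: "While impressive, these positive outcomes were measured using patient symptom scores". It continues: "we propose to assess the objective improvement in nasal airflow secondary to the VivAer procedure". Study Design repeats the aim: "This is a prospective, non-randomized trial to assess objective improvement in nasal patency after undergoing treatment of the nasal valve with VivAer". Expected Benefits looks to the same evidence: "The objective data received from this study will help clinicians provide better guidance to patients interested in receiving this treatment".

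**Aims.** The general statement under Specific Aims covers both kinds of outcome without ranking them: "Eligible patients will show significant clinical improvement on the following patient questionnaires and on objective measurements". Aim 2 is NOSE and Aim 3 is SNOT-22. No Aim 1 appears in the text supplied.

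**Efficacy.** The last paragraphs of Description of Procedure say: "Efficacy endpoint will be determined at 26 weeks using the NOSE and SNOT survey scores". A responder is defined by a fall of at least 15 points in score. PNIF follows as a further measurement at the same time points, with no threshold or decision attached.

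**Analysis.** Statistical Analysis applies a paired t-test or McNemar's test to the outcomes, objective measurements included. It names no primary outcome and does not say which outcome the 26 patients are meant to power.

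**Design.** The introduction calls the study open-label, and Study Design calls it non-randomized. Entry is by symptom score: "Nasal obstruction, defined as" 60 or more on the NOSE scale.

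**The concern.** The trial is justified by a gap in objective evidence, but the endpoint that decides efficacy is of the kind said to have left that gap. Patients know they were treated, there is no comparator, and NOSE serves both as an entry threshold and as part of the endpoint. Expectation, and regression to the mean after selection on a high score, can lower NOSE without any change in airflow. PNIF is also measured open-label, so the contrast is between objective and self-reported outcomes, not between blinded and unblinded ones.

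At stake is what the trial can conclude. With no ranking, a positive symptom result meets the endpoint as written whatever PNIF shows. Choosing the deciding outcome after the results are seen would not be credible.

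**Working it through.** **1. Purpose against endpoint**

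| Section | Outcome it points to |
|---|---|
| Introduction | Objective airflow; symptom scores named as the limit of earlier work |
| Study Design | Objective nasal patency |
| Specific Aims, general statement | Questionnaires and objective measurements, unranked |
| Description of Procedure, efficacy paragraph | NOSE and SNOT; PNIF listed afterwards |
| Statistical Analysis | All outcomes, none primary |
| Expected Benefits | Objective data |

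Only the efficacy paragraph says how efficacy is determined, and it does not use the objective measure.

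**2. Can the sample size show which outcome was intended?** No. The effect size d = 0.50 is standardized, so the calculation is the same for PNIF, NOSE or SNOT-22. The plan gives no standard deviation or expected change for PNIF.

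**3. The plan's power figure.** Inputs from Statistical Analysis: n = 26, alpha = 0.05, two-sided tests, d = 0.50, paired t-test, stated power 80%.

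The exact calculation uses the noncentral t distribution with n − 1 = 25 degrees of freedom and noncentrality d × √n = 0.50 × √26 = 2.55.

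- Two-sided 0.05: power 68.8%. The stated 80% is not reproduced.
- One-sided 0.05: power 79.8%. This matches the stated figure but contradicts the two-sided tests specified.
- Two-sided, 80% power at d = 0.50: 34 patients (33 give 79.5%, 34 give 80.8%). The normal approximation gives ((1.960 + 0.842)/0.50)² = 31.4, so 32.
- Two-sided, 80% power with 26 patients: d = 0.572.
- Dropout: Study Design caps enrolment at 26 with no allowance. Assuming about 10% loss, 26 × 0.9 = 23.4, so 23 evaluable patients, and two-sided power at d = 0.50 is 63.0%.

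**4. Is there one final visit and one baseline?**

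- Final visit: the efficacy paragraph says 26 weeks. Study Design says 24 weeks, and the Study Calendar says 24 weeks ± 2, that is 22 to 26. Week 26 is the edge of that window, not its target.
- Baseline: Study Design places baseline PNIF, NOSE and SNOT-22 on the procedure date. The Study Calendar marks them under Consent and leaves the Procedure column blank.

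A primary change from baseline cannot be defined until both are reconciled.

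**The case against.** The strongest reply is that PNIF is unranked rather than demoted. It is collected at every follow-up alongside the questionnaires, the general aim includes it and the paired tests cover it. No section uses the word primary. This stands, and it rules out two stronger readings:

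- A reader might infer that the trial would produce no objective evidence, or would simply repeat the limitation of the earlier studies. It would not: a null PNIF result would be reported beside the symptom scores. The risk is that the efficacy conclusion rests on the wrong outcome.
- A reader might want a probability of symptom success with no PNIF effect as the size of the defect. With true PNIF change set to zero, PNIF is non-significant in 95% of trials by construction. For NOSE alone at d = 0.50, and assuming independence, the result is 0.688 × 0.95 = 0.65. That is essentially symptom-score power, and the same data would arise equally often after the fix.

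Two further objections carry part weight. Aim 1 may have been PNIF and been lost from the supplied text, so its absence is not counted as a fault; if it was PNIF, the efficacy paragraph conflicts with the lead aim as well. And repeating NOSE on the procedure date, as Study Design describes, could reduce regression to the mean. The Study Calendar does not show that repeat, the size of the effect cannot be computed from the documents, and expectation remains.

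**Conclusion.** The concern holds in this form: the only efficacy endpoint does not match the purpose stated in the introduction and Study Design, and no ranking of outcomes corrects it. Efficacy as defined could be declared on self-report while the objective question is left undecided. This is a finding about the text and depends on no assumed effect or correlation. It should be settled before outcome data are examined.

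The figure that does need correcting is the power. It is about 69% two-sided at n = 26 and d = 0.50, against a stated 80%, and about 63% if 23 are evaluable (dropout assumed). Applying d = 0.50 to PNIF is itself an assumption, since the plan gives no basis for it.

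**What to change.** In the efficacy paragraph and in Statistical Analysis:

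1. Name change in PNIF from one defined baseline to one final visit as the primary endpoint, tested by paired t-test at two-sided 0.05.
2. Make mean change in NOSE, mean change in SNOT-22 and the 15-point responder rate secondary at that visit.
3. Reconcile 26 weeks with 24 ± 2 weeks, and the procedure-date baseline with the consent-visit baseline, so that the endpoint has one of each.
4. Restate the power sentence for PNIF: 26 evaluable patients give about 69% two-sided power at d = 0.50, or 80% at d = 0.57, and less with dropout. State that d for PNIF is assumed.

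Rewriting the purpose around symptom scores would also remove the inconsistency, but it would give up the reason the protocol offers for the trial.

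**Cost.** The change re-ranks measurements already scheduled and keeps the cap of 26, so it adds no visits, measurements or patients. The symptom scores become secondary and the stated power is less favourable. Keeping 80% two-sided power at d = 0.50 would instead need 34 evaluable patients.

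**Optional.** A confidence interval for the responder rate, reporting weeks 4 and 12 as estimates, and the correlation of PNIF change with symptom change would be useful, but this point does not depend on them.
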